1.0 PROTOCOL SUMMARY AND/OR SCHEMA

TARGET PATIENTS

- Locally advanced or metastatic solid tumors, and
- Chemotherapy Induced Thrombocytopenia,
 - Thrombocytopenia has persisted for at least 4 weeks despite:
 - > Delay in chemotherapy, and/or
 - Modification of chemotherapy dose/regimen.
- Meets Inclusion/Exclusion criteria
- No mutations associated with myelodysplasia or leukemia by peripheral blood bone marrow cytogenetics and FISH panel.

Romiplostim (Weekly, SQ Treatment) Initial dose: 2 mcg/kg, then titrate per protocol section 9.0, "Treatment/ Intervention Plan"

- Weekly monitoring on Romiplostim per section 9.0, "Treatment/ Intervention Plan:
- First 3 weeks on treatment: Weekly CBC, COMP, LDH, PT, aPTT
- Maintenance on Treatment: Weekly CBC and monthly Comprehensive Chemistry Panel, LDH, PT, aPTT

Primary Endpoint: At 3 Weeks	Proportion of patients achieving ≥100,000/mcL platelets by the end of 3 weeks of treatment.				
Within 3 weeks	Romiplostim (Treatment)				
<100,000/mcL	Failure: terminate from study or continue at the discretion of the investigator.				
≥100,000/mcL	Success: Continue romiplostim at the discretion of the investigator and oncologist.				

At Successful Achievement of Primary Endpoint: Achieve a platelet count of ≥100,000/mcL within 3 weeks.

- Resume chemotherapy regimen at the discretion of the oncologist.
- > Continue weekly romiplostim

Secondary Endpoints:

- 1. Ability to resume and continue two cycles (or 8 weeks, whichever comes first) of chemotherapy without recurrence of Chemotherapy-Induced Thrombocytopenia. We will also observe the following events:12 months of chemotherapy without recurrence of Chemotherapy-Induced Thrombocytopenia.
- 2. Change in chemotherapy regimen for toxicity unrelated to thrombocytopenia.
- 3. Change in chemotherapy regiment for progression of disease or other cancerrelated conditions.
- 4. Death from any cause.

NOTES:

- All Romiplostim treatment will be given as weekly, subcutaneous injections, and doses titrated per protocol section 9.0, "Treatment/ Intervention Plan".
- After the initial 3 weeks of romiplostim on romiplostim, patients who remain on weekly romiplostim will continue to have routine monitoring of weekly CBC and monthly COMP, LDH, and PT/aPTT at discretion of study investigator or oncologist.
- ➤ Patients who remain on Romiplostim for 4 or more months, will undergo one marrow aspirate and biopsy or peripheral blood test, with cytogenetics, and FISH panel for MDS, in the 30 day period after completion of the 4th month.
- > Throughout this protocol, to allow for patient scheduling limitations and needs, treatment schedules will be 7 days +/- 2 days.
- Treatment can be held up to 16 days if patient develops an intercurrent medical illness or symptom that is unrelated. Treatment may be held up to 20 days if the patient is unavailable for non-medical reasons, such as vacation or travel.
- If the patient receives romiplostim therapy for ≥12 months, the scheduling of routine labs and treatment dosing will be at the discretion of the investigator.

2.0 OBJECTIVES AND SCIENTIFIC AIMS

The primary objective for this study is:

 To evaluate whether romiplostim can improve the recovery of persistent, isolated Chemotherapy-Induced Thrombocytopenia (CIT), to a platelet count ≥100,000/mcL within 3 weeks after initiation of therapy.

Secondary Objectives

The secondary objectives for this study are:

- 1. In patients whose platelet counts have recovered within three weeks on romiplostim treatment, we will observe for:
 - a. Ability to resume at least two cycles (or eight weeks, whichever comes first) of chemotherapy without recurrence of chemotherapy-induced thrombocytopenia leading to chemotherapy dose delay or reduction.
 - i. Note the duration of off-chemotherapy time.
 - b. Change in chemotherapy for progression of disease or other cancer related conditions.
 - c. Change in chemotherapy for other toxicities unrelated to thrombocytopenia.
 - d. Censor patients who have tolerated chemotherapy with romiplostim support for up to 12 months.
 - e. Death due to all causes.
- 2. The safety profile of romiplostim will be assessed in this patient population at specified time-points during the course of study as per section 11.0 Toxicities/Side Effects.

3.0 BACKGROUND AND RATIONALE

3.1 Chemotherapy-induced thrombocytopenia

Chemotherapy-induced thrombocytopenia (CIT) is defined as a single hematopoietic lineage depression resulting in a low platelet count (< 100,000/mcL) despite adequate recovery time from prior chemotherapy. Not uncommonly, CIT can result in subsequent dose reductions and can adversely affect on time delivery of subsequent chemotherapy cycles. In a retrospective series of 609 patients with solid tumors or lymphoma who exhibited CIT (platelets of <50,000/mcL), delay in subsequent chemotherapy occurred during 6% of cycles. The CIT cohort used more resources, but outcomes were not impacted when compared to those who did not experience CIT¹. In the same report, dose reduction occurred in 15% of patients with CIT ¹. Currently, the management of CIT is supportive with platelet transfusions per the discretion of the treating medical oncologist. Presently, there is no specific standard of care for CIT.

3.2 Romiplostim: Mechanism of action

Romiplostim (Npate®) is a thrombopoietin (TPO) mimetic that is Food and Drug Administration (FDA) approved for use in patients with chronic immune thrombocytopenia (ITP) ². Romiplostim bears no structural or biochemical resemblance to TPO, but mimics the TPO binding to the TPO receptor (Mpl). ³ Romiplostim is a 'peptibody' formed by the fusion of the Fc portion of an IgG1 monoclonal antibody with four TPO mimetic peptides. Romiplostim binds the distal cytokine homology region of the TPO receptor leading to activation of the JAK/STAT pathway. Simultaneously, romiplostim has been shown to engage the MAP kinase pathway leading to activation of anti-apoptotic pathways resulting in increased platelet production^{4,5}.

3.3 Romiplostim: Clinical activity

Romiplostim has been shown to increase and maintain platelet counts in splenectomized and non-splenectomized patient with ITP with few adverse effects. ⁶ No anti-TPO antibody formation of clinical significance has been reported to date. ⁶ In several trials of patients with ITP, the mean therapeutic dose of romiplostim to achieve a platelet count of 50-200,000/mcL was 3-4 mcg/kg. ⁵

3.4 Rationale for Romiplostim in CIT

At MSKCC, [name], [name], and [name] have treated over 50 patients with romiplostim for CIT. Our initial case series of 20 patients was published in 2014, indicating 19 of 20 treated patients meeting the goal of normalization of platelet count to >100,000/mcL ([name] et al, 2014).

Our interim observations of this current clinical trial suggests that romiplostim is effective and safe to improve platelet counts in patients with CIT. Of the treatment patients, 13 of the 14 (93%) romiplostim patients normalized their platelet count within the three-week primary endpoint. From our initial 21 patients who enrolled on this trial, 1 out of 7 (14.3%) observation patients have corrected her platelet counts within 3 weeks. (P= 0.0009 by two-tailed Fisher's Exact Test). Of the 5 observation patients who crossed over to romiplostim and were evaluable, all 5 corrected their platelet count within 3 weeks. Of all patients receiving romiplostim, 18 of 19 patients (95%) reach platelet counts of 100,000/mcL or greater within 3 weeks of treatment. No patients who resumed chemotherapy while receiving romiplostim (N=14) had a recurrence of CIT. We continue to see efficacy and safety within our patients currently on romiplostim. Based on highly significant efficacy and no further spontaneous correction of platelets, it was felt inappropriate to continue randomizing to the observation control arm.

No toxicity attributable to the romiplostim has been observed in our initial cases. Three of the initial 20 courses of treatment (19 patients) developed deep vein thrombosis which is within the historical range of between 10% and 30% ⁷ in comparable patients with metastatic cancer on chemotherapy. Further, one of the two patients with DVT had a previous history of DVT, prior to initiation of romiplostim, and had been off anticoagulation when the second thrombosis occurred.

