7.0 RECRUITMENT PLAN

This study will be conducted at MSKCC and participating institutions. Potential research subjects will be identified by members of the solid tumor oncology services. Fortunately, this will be based on existing referral patterns to the Hematology Service.

After the consultation and results of the cytogenetics and FISH, if a patient qualifies for the trial, the consulting hematologist will discuss the possibility of participation in the study. If consent is offered, the risks: benefits will be presented to the patient by an investigator prior to the patient consenting. If the patient consents, they will be enrolled by a study RSA (see section 15.1). Similar recruitment procedures will be followed at participating institutions.

This study does not compete with any existing or planned other studies for CIT and therefore, we anticipate a high percent of the appropriate patients will be referred. It is expected that a total of 60 patients will be recruited to this study.

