11.0 TOXICITIES/SIDE EFFECTS

Based on our initial experience, we have not observed treatment-related toxicities in our first 40+ patients. Based on the romiplostim Prescribing Information, the most common adverse

reactions (≥5% higher patient incidence in romiplostim versus placebo) are arthralgia, dizziness, insomnia, myalgia, pain in extremity, abdominal pain, shoulder pain, dyspepsia, and paresthesia.

Individual cases of thrombosis and been reported in patients receiving romiplostim, but in one recent review of long-term use of romiplostim, "The thrombotic adverse event rate across all studies was 0.09 events per 100 patient-weeks on romiplostim therapy," markedly lower than would expected in patients with active cancer receiving chemotherapy. We have not observed an increased thrombosis rate compared with expected rates in patients with metastatic cancer, on chemotherapy, however, we will monitor any clinical evidence of thrombosis as well as hemorrhage.

Assessment of potential toxicity will be based on the Common Terminology Criteria for Adverse Events (CTCAE) Version 4.0. We will monitor for evidence of marrow toxicity, with weekly CBC (CBC must include: WBC, Hgb, platelet, MCV, cell differential) and lab toxicities of grade 3/4 will be adjudicated on a regular basis by the PI or Co-PI of the study. In addition, cytogenetics testing through bone marrow aspirate or peripheral blood will be performed within 30 days after the completion of the 4th month on treatment.

Patients will be monitored for Adverse Events throughout the study at the following time points: Toxicity Assessments will be completed at 3-weeks from enrollment (3-weeks from initiation of romiplostim in cross-over patients), and every 3 months while on romiplostim. A final toxicity assessment will be completed 1 month after the last dose of romiplostim. However, if the patient is discontinuing chemotherapy and going to hospice/ comfort care, the final toxicity assessment will be omitted if toxicities were managed regularly. For purposes of toxicity assessment, 3 months will be defined as 90 days +/- 15 days, 1 month is defined as 30 days +/- 15 days, and 3 weeks will be defined as 21 days + 9 days.

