14.0 BIOSTATISTICS

This study was originally designed as a phase II randomized study where patients were randomized 2:1 to respectively receive romiplostim and observational control. The primary endpoint was the achievement of a platelet count of ≥ 100,000/mcL within three weeks of study enrollment, and any patient removed from study during evaluation window without count recovery was considered a treatment failure. Based on earlier MSKCC data, it was estimated that the probability of a success in the romiplostim arm is at least 90%, while the probability of a spontaneous recovery in the control arm is 60% or less.

Due to preliminary trial results, the protocol was amended on 4/13/2016 and the observation control arm was dropped. At that point, the study became a single arm phase II study of romiplostim. The sections below represent the new single arm study design.

Analysis of these data will only be done with 60 evaluable patients enrolled on the trial. There was one patient enrolled during this time who was inevaluable and therefore there were 61 patients enrolled for 60 spots.

Primary endpoint:

This study is a single arm phase II design to evaluate romiplostim mediated improvements in platelet counts in patients who have experienced CIT. The primary endpoint is the achievement of a platelet count of ≥ 100,000/mcL within three weeks of study enrollment. Any patient who is removed from study before the evaluation of the primary endpoint will be considered a treatment failure. A total of sixty patients will be enrolled and treated with romiplostim. Based on preliminary MSKCC data, it is estimated that the probability of a success in patients on romiplostim treatment is at least 90%. Therefore, we will consider the trial promising and worthy of further intervention if at least 54 out of 60 achieve platelet count recovery. The operating characteristics of this design rule are provided in the table below.

	True Rate of Count Recovery						
Probability of	0.85	0.875	0.9	0.925	0.95		
Observing >= 54/60	17%	40%	60%	81%	97%		

Secondary endpoints:

Patients who achieve a platelet recovery may be allowed to resume chemotherapy. In these patients, we are observing for recurrence of chemotherapy-induced thrombocytopenia leading to chemotherapy dose delay or reduction; change in chemotherapy for progression of disease or other cancer related conditions; change in chemotherapy for other toxicities unrelated to thrombocytopenia; and death due to all causes.

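### Section 14 does not say whether the randomised-phase romiplostim patients count among the 60; if they do, the tabulated pass probabilities for the 54/60 rule do not apply

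*Combined protocol and SAP*

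**What the plan says.** Section 14 records that the trial began as a 2:1 randomised comparison and that the control arm was dropped by an amendment dated 4/13/2016, because of preliminary trial results. Section 3.4 gives those results for the first 21 patients, whom it describes as enrolled on this trial. On romiplostim, "13 of the 14 (93%) romiplostim patients normalized their platelet count" within three weeks; on observation 1 of 7 did. All 5 evaluable cross-over patients recovered, making 18 of 19 among everyone treated.

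For the single-arm design, Section 14 says "we will consider the trial promising and worthy of further intervention if at least 54 out of 60 achieve platelet count recovery". It then adds "The operating characteristics of this design rule are provided in the table below": 17%, 40%, 60%, 81% and 97% at true rates of 0.85, 0.875, 0.90, 0.925 and 0.95.

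The 60 are described differently in different places:

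- Section 14, before the endpoint text: "Analysis of these data will only be done with 60 evaluable patients enrolled on the trial". It adds that 61 were enrolled for 60 places because one patient was inevaluable, over a period whose start is not given.
- Section 14, primary endpoint: "A total of sixty patients will be enrolled and treated with romiplostim".
- Section 7: "It is expected that a total of 60 patients will be recruited to this study".

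The three-week clock also varies. Section 14 starts it at study enrolment; Section 4.1 starts it at initiation of romiplostim.

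**The concern.** The 54/60 rule is the only efficacy decision rule in the single-arm plan. Section 14 gives no null rate and no alpha for it, so the table is the only statement of how demanding the rule is. That table treats the outcomes of all 60 patients as unknown when the rule is set. The outcomes of the first 14 romiplostim patients were known by then.

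The wording about patients enrolled on the trial, and Section 7's study total of 60, can be read to include those 14. The wording about sixty who will be enrolled and treated can be read to exclude them. If the choice is left open, it may be made after the results are in. The pass or fail answer can depend on it, and under the inclusive reading the published pass probabilities describe a different design from the one carried out.

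**Working it through.** **Inputs.** Rule: at least 54 of 60 (Section 14). True rates 0.85 to 0.95 and the stated pass probabilities (Section 14 table). Known results: 13/14 on randomised romiplostim, 18/19 including cross-overs (Section 3.4).

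**Step 1. Reproduce the table, taking 60 new patients.** The formula is the exact binomial tail P(X ≥ 54), X ~ Bin(60, p). The results are in the third column below. The entries at 0.85, 0.90 and 0.95 agree with the plan to within 2 points. Those at 0.875 (40% stated, 36.4% exact) and 0.925 (81% stated, 83.9% exact) do not. A strict inequality, 53 or more of 60, a denominator of 61, and normal approximations with and without continuity correction do not reproduce all five either. This is a separate arithmetic matter; the type of calculation is right for 60 new patients.

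**Step 2. Count the 14 randomised romiplostim patients.** New patients: 60 − 14 = 46. Successes still needed: 54 − 13 = 41. The pass probability given the known results is P(X ≥ 41), X ~ Bin(46, p).

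| True rate | Stated | 60 new, exact | 13/14 carried in | Shift (points) |
|---|---|---|---|---|
| 0.85 | 17% | 0.1848 | 0.2933 | 10.8 |
| 0.875 | 40% | 0.3643 | 0.4782 | 11.4 |
| 0.90 | 60% | 0.6065 | 0.6897 | 8.3 |
| 0.925 | 81% | 0.8387 | 0.8721 | 3.3 |
| 0.95 | 97% | 0.9703 | 0.9737 | 0.3 |

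**Step 3. Can the decision differ?** Yes. With 41 successes in 46 new patients, the new patients alone show 41/46 = 89.1%, below the 54/60 = 90.0% standard. Pooled with 13/14 they give 54/60 and pass.

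**Step 4. Secondary sensitivity, 18/19 carried in.** Needed: 54 − 18 = 36 of 60 − 19 = 41. The pass probability is 40.7% at 0.85, 77.7% at 0.90 and 98.4% at 0.95. This requires counting the 5 cross-overs from the start of romiplostim, which is not the Section 14 clock.

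**Step 5. Precision if only post-amendment patients are used.** Exact (Clopper-Pearson) 95% intervals: 41/46 gives 76% to 96%; 54/60 gives 79% to 96%.

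**The case against.** The best defence is that the text favours 60 new patients. Section 14 introduces the relevant part as the new single-arm design and speaks of sixty who will be enrolled and treated. Sections 4.1, 4.2 and 9.0 give 60 on romiplostim, and Section 15.2 says there is no randomisation. Section 7 is prospective too. The note on 61 patients for 60 places follows the announcement of the new design, so its period most naturally means the single-arm phase. Nor do the figures fit easily with counting all 21: only 5 of the 7 observation patients had crossed over and were evaluable, so 2 lacked a romiplostim result at the interim. Had all 21 been among the 61, at most 59 would be evaluable on romiplostim unless those 2 were treated later.

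Most of this stands, and it makes the new-patients reading the more likely one. It does not close the gap. No passage states the restriction, the 61-for-60 period has no start date, and the count of 59 says nothing against including only the 14 randomised to romiplostim.

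A reader might infer four stronger things that the documents do not support:

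- **That the tabulated probabilities are wrong for this reason on any reading.** They fail for this reason only if known results are carried in.
- **That the bar was set from 13/14.** Section 14 shows 90% was already the romiplostim assumption in the randomised design, and 54/60 is exactly 90%. Section 3.4 attributes dropping the control arm to efficacy together with the lack of spontaneous recovery on observation.
- **That a pass is impossible** because 13 + 1 + 39 = 53. This scores untreated observation weeks, whereas Section 14 requires treatment with romiplostim, Section 4.1 counts from initiation, and Section 12 limits the endpoint to patients who receive it.
- **That the cross-overs are shown to be in the 60.** The phrase "3-weeks from initiation of romiplostim in cross-over patients" in Section 11 concerns the timing of toxicity assessments only.

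**Conclusion.** The point holds conditionally. Membership of the 60 is not defined by date or arm, and the two descriptions in Section 14 point in different directions. If the 14 randomised romiplostim patients are counted, the chance of passing rises by 10.8 points at a true rate of 0.85 and by 8.3 points at 0.90, and results such as 41/46 in new patients pass only by pooling. At 0.95 the effect is negligible. If all 60 are new, there is no such effect and the table needs only its two inexact entries corrected.

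The figures assume independent patients with a common recovery rate, and that exactly the 14 patients in Section 3.4 are carried in. The documents do not say whether others were randomised between that interim look and the amendment. Because the single-arm design states no null rate, these are pass probabilities at given true rates, not type I error rates. The 18/19 figures are a secondary sensitivity at most.

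**What to change.** State in Section 14 that the 54/60 rule and its table apply to evaluable patients registered after 4/13/2016 and treated with romiplostim, and that randomised-phase patients, including cross-overs, are reported separately and do not count toward the 54. Align Section 7 and the sentence about evaluable patients with this, and give the start of the period in which 61 were enrolled. Recalculate the table, including the entries at 0.875 and 0.925.

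If earlier patients already fill some of the 60 places, say how many and from which arm. Make the post-amendment proportion with its exact 95% interval the main estimate, show the pooled result as supportive, and restate the pass probabilities conditional on the known results.

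Reconcile the endpoint clock between Section 14 (enrolment) and Section 4.1 (initiation), so that one definition applies throughout.

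The cost is a few sentences in Section 14, a recalculated table and one extra line in the results. No new data are needed. If earlier patients do hold places, the main estimate rests on fewer patients and its interval is slightly wider, as in the example of 76% to 96% against 79% to 96%.

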4.0 OVERVIEW OF STUDY DESIGN/INTERVENTION

4.1 Design

Primary objective:

This is an intent-to-treat multicenter phase II open label trial. Once appropriate patients are identified and enrolled, 60 patients will be enrolled.

During the initial 3-week period, the enrolled patients will receive romiplostim, titrated as per protocol (Section 9.0). Assessment for the primary endpoint will take place at week 3 and denote the proportion of patients that achieves a platelet count of >100,000/mcL within 3 weeks of initiation.

Safety Analysis will be performed at specified time-points (Section 11.0 Toxicities/Side Effects) including possible adverse events such as thrombosis, peripheral blood abnormalities and evidence of organ dysfunction.

Secondary objective:

In patients whose platelet counts have recovered within three weeks, we will observe for patient's ability to receive two cycles (or eight weeks, whichever comes first) of cytotoxic chemotherapy without recurrence of chemotherapy-induced thrombocytopenia leading to chemotherapy dose delay or reduction; change in chemotherapy for progression of disease or other cancer related conditions; change in chemotherapy for other toxicities unrelated to thrombocytopenia; and death due to all causes. The duration for patients off-chemotherapy will also be noted. In addition we are also censoring patients who have tolerated chemotherapy with romiplostim support for up to 12 months.

Safety endpoints will include possible adverse events such as thrombosis, evidence of marrow toxicity, and evidence of organ dysfunction.

